8.7.1 Treatment accountability and compliance

Accounting and compliance for IMPs will be performed at Visit 3 and all subsequent on-treatment, on-site visits.

The Investigator will check the compliance to the IMP dose schedule based on the patient diary and will then complete the appropriate Site treatment and patient treatment log forms. Returned IMP will be counted by site staff. In addition the dosing information will be recorded on the appropriate pages of the e-CRF.

For NIMPs sulfonylurea and (if applicable) metformin, name, start and end date of treatment, total daily dose, etc, will be documented in the source documents. Compliance to sulfonylurea and metformin will be checked by interviewing the patient and reviewing the patient diary at each visit and documented in the source documents and in the e-CRF.

Rescue therapy (see [Section 8.2.2](#)) is to be reported in the e-CRF. This information should include specific drug name, dose, route of administration, and frequency.

If compliance is inadequate as determined by the Principal Investigator (PI), patients will be trained again and mentored. If suboptimal compliance continues after training and mentoring, patients may be discontinued at the discretion of the PI after discussion with the Sponsor/CRO's medical monitor.

8.7.2 Return and/or destruction of treatments

Patients are to return all IMP (unused, in use or empty bottle[s]) at each on-site visit (or final assessment on-treatment visit in case of permanent premature discontinuation), as described in [Section 1.2](#).

All used, partially-used or unused IMPs will be retrieved by the Sponsor or Delegate. A detailed site and patient treatment log of the returned IMP will be established with the Investigator (or the pharmacist) and countersigned by the Investigator and the monitoring team.

For NIMP not provided by the Sponsor (ie, sulfonylurea, metformin, and rescue therapy), tracking is to be undertaken by the Investigator (or pharmacist if appropriate) according to the system proposed by the Sponsor/CRO.

8.8 CONCOMITANT MEDICATION

A concomitant medication is any treatment received by the patient concomitantly to any IMP. The IMP includes placebo and sotagliflozin 400 mg.

All concomitant medications should be documented on the Medications page of the e-CRF. This includes all NIMP treatments that are taken by the patients at any time during the clinical trial, beginning at Visit 1.

Additionally, all medications taken in the 3 months prior to Visit 1 and prior use of SGLT2 inhibitors should be reported.

8.8.1 Prohibited prior and concomitant medications

During the study treatment period, the following medications are prohibited:

- Initiation of any antidiabetic agents, including oral or injectable antihyperglycemic agents other than the IMP before the rescue therapy
Note: short-term use (<10 consecutive days) of the prohibited medication, eg, short-acting insulin for treatment of acute illness or surgery is allowed.
- Systemic use of glucocorticoids for more than 10 consecutive days (topical, ophthalmic, nasal spray or inhaled applications are allowed)
- Initiation of any weight loss drugs (eg, phentermine, orlistat)
- Investigational medicinal products in any other clinical study

SGLT2 inhibitors (eg, canagliflozin, dapagliflozin, or empagliflozin), additional sulfonylurea and metformin are not allowed for rescue or post IMP therapy until the end of study.

Reduction of digoxin dose should be considered because sotagliflozin acts as a weak P-gp inhibitor and increases systemic exposure to digoxin. Patients taking sotagliflozin with concomitant digoxin should have digoxin concentrations monitored and doses reduced as needed.

In addition, other P-gp substrates may be affected and the labels of P-gp substrate drugs should be consulted with regards to monitoring and dose adjustments.

Other medications which are unlikely to interfere with the PK or PD of the IMP or confound interpretation of the study endpoints are allowed as needed following discussion between the Investigator and the Sponsor/CRO. However, doses of chronically administered medicines should be kept fixed during the trial if at all possible.

After premature permanent discontinuation of the IMP, any treatments (other than SGLT2 inhibitors, and additional sulfonylurea and metformin) are permitted, as deemed necessary by the Investigator.

The dose of all antihypertensive agents should be kept constant during the 12 weeks following randomization and no antihypertensive agents should be added or withdrawn for the 12 weeks following randomization unless it is considered necessary for safety reasons.

8.8.2 Concomitant diabetes therapy

For patients in both groups, background sulfonylurea and (if applicable) metformin should be stable throughout the study unless down-titration is required for safety reasons.

The rescue medication(s) that will be used to treat hyperglycemia when a patient's hyperglycemia reaches the rescue threshold are also defined as NIMPs. Except for SGLT2 inhibitors, additional metformin and sulfonylurea, any approved medication(s) including oral antidiabetic drugs, GLP-1 receptor agonists, or insulin can be prescribed at the Investigator's discretion to treat the hyperglycemia. Metformin will also be permitted for patients on sulfonylurea only at Screening. The regimen of the rescue medications will be in accordance with local standard of care and prescribing practice.

8.9 POSTSTUDY TREATMENT

Because sotagliflozin may reduce BP, adjustment of antihypertensive medication may be needed during the study in patients with hypertension. Conversely, monitoring for an increase in BP should be performed after withdrawal of study medication. If the BP is elevated after withdrawal of study treatment, the Investigator should consider adding or adjusting antihypertensive medication.

9 ASSESSMENT OF INVESTIGATIONAL MEDICINAL PRODUCT

9.1 EFFICACY ENDPOINTS

9.1.1 Primary efficacy endpoint

- Change from Baseline to Week 26 in HbA1c (%)

9.1.2 Secondary efficacy endpoints

The continuous secondary efficacy endpoints are:

- Change from Baseline to Week 26 in FPG
- Change from Baseline to Week 26 in body weight
- Change from Baseline to Week 12 in SBP for patients with Baseline SBP ≥ 130 mmHg
- Change from Baseline to Week 12 in SBP for all patients
- Proportion of patients with HbA1c $< 6.5\%$, $< 7.0\%$ at Week 26

9.1.3 Other efficacy endpoints

- Change from Baseline to Week 12 in SBP for patients with Baseline SBP < 130 mmHg
- Proportion of patients with reduction in body weight by $\geq 2\%$, $\geq 5\%$, and $\geq 10\%$ from Baseline
- Change from Baseline to Week 12 in DBP
- Proportion of patients achieving SBP < 130 mmHg for those with Baseline SBP ≥ 130 mmHg
- Proportion of patients achieving DBP < 80 mmHg for those with Baseline DBP ≥ 80 mmHg
- Proportion of patients requiring rescue for hyperglycemia
- Change from Baseline in:
 - Serum creatinine
 - eGFR
- Change from Baseline to Week 79 in HbA1c
- Change from Baseline to Week 79 in FPG
- Change from Baseline to Week 26 in SBP for all patients and for patients with Baseline SBP ≥ 130 mmHg
- Change from Baseline to Week 79 in SBP for all patients and for patients with Baseline SBP ≥ 130 mmHg
- Change from Baseline to Week 79 in body weight

9.1.4 Assessment methods of efficacy endpoints

9.1.4.1 Hemoglobin A1c

Hemoglobin A1c will be assessed at Screening (Visit 1) and all on-site visits during the double-blind treatment period with the exception of Week 18 (Visit 8).

For the eligibility and efficacy assessments of the study, HbA1c is measured by a certified level I “National Glycohemoglobin Standardization Program” central laboratory to allow estimation of the change from Baseline to Week 26 in HbA1c and the proportion of patients with HbA1c <6.5%, <7.0% at Week 26.

If a patient needs to receive rescue antidiabetic medication, assessment of HbA1c should be performed before the introduction of the rescue medication.

9.1.4.2 Fasting plasma glucose measurement

Plasma glucose is measured in the fasting state at Screening (Visit 1) and all on-site visits during the treatment period. For the eligibility and efficacy assessments of the study, FPG is measured at a central laboratory to allow estimation of change from Baseline to Week 26 in FPG.

9.1.4.3 Body weight measurement

Body weight is measured at all on-site Visits. Body weight will be measured to allow the estimation of change from Baseline to Week 26 in body weight and reduction in body weight by $\geq 2\%$, $\geq 5\%$, and $\geq 10\%$ from Baseline.

Body weight should be obtained with the patient wearing undergarments or very light clothing and no shoes, and with an empty bladder. The same scale should be used throughout the study, and calibrated on a regular basis as recommended by the manufacturer. Calibration documents should be filed in the study file.

The use of balance scales is recommended. The floor surface on which the scale rests must be hard and should not be carpeted or covered with other soft material. The scale should be balanced with both weights at zero and the balance bar aligned. The patient should stand in the center of the platform as standing off-center may affect measurement. The weights are moved until the beam balances (the arrows are aligned). The weight is read and recorded in the e-CRF and Source Data. Self-reported weights are not acceptable; patients must not read the scales themselves.

9.1.4.4 Blood pressure endpoint measurements

Systolic BP and DBP will be assessed at all on-site visits. Blood pressure measurements must be taken as described in [Section 9.2.1.4](#) with details provided in [Appendix C](#).

9.1.4.5 Kidney function parameter measurement

Serum creatinine will be assessed at Baseline (Visit 3) and selected on-site visits (see Study Flowchart in [Section 1.2](#)). A central laboratory will analyze samples and estimate change from Baseline in serum creatinine and eGFR.

9.1.4.6 Proportion of patients requiring rescue for hyperglycemia

The use of rescue medications for hyperglycemia will be assessed and reported throughout the treatment period. Routine alerts on FPG and/or HbA1c will be sent to the Investigator from the central laboratory to ensure that glycemic parameter results remain within predefined thresholds. For details and further actions should FPG and/or HbA1c values fall above thresholds, refer to [Section 8.2.2](#).

9.2 SAFETY ENDPOINTS

Assessments for safety include AEs, SMBG, clinical laboratory assessments, physical examination, electrocardiogram (ECG), weight, and vital signs. An independent DMC will meet on a regular basis to review accumulating clinical trial safety data.

Adjudication of all deaths, MACE/other selected CV events (MI, stroke, unstable angina leading to hospitalization, and heart failure leading to hospitalization), selected renal events, bone fracture, and DKA will be performed in a blinded manner by a CEC(s) comprised of experts. Details will be provided in the charter of the CEC(s). Further details are available in [Section 6.4](#).

Two expert committees will review all potential cases of DILIs and cases of amputation in a treatment-blinded manner to evaluate causality.

The following safety endpoints will be assessed:

- Adverse events, AEs leading to discontinuation from the IMP, adverse events of special interest (AESIs), events of special interest (EOSIs), SAEs and deaths
- Hypoglycemia (all, severe, and/or documented symptomatic hypoglycemia)
- Clinical laboratory results (including fasting lipids; see [Section 9.2.1.3](#))
- Vital signs and ECG results.

Observation period of safety endpoints

The observation period of safety data will be divided into 3 segments:

- The pre-treatment period is defined as the time between the date of the informed consent and the first dose of double-blind IMP
- The on-treatment period (TEAE period) is defined as the time from the first dose of double-blind IMP up to 10 days (1 day for hypoglycemia) after the last dose of double-blind IMP, regardless of the introduction of rescue therapy. The 10-day interval is

chosen based on the half-life of the IMP (approximately 5 times the half-life of sotagliflozin in patients with moderate renal dysfunction)

- The post-treatment period is defined as the time starting 11 days after the last dose of double-blind IMP (after the on-treatment period)

The Baseline value for safety endpoints in the safety population is the last available value (or the average of all values for creatinine or eGFR) prior to the first administration of double-blind IMP.

9.2.1 Assessment methods of safety endpoints

9.2.1.1 Adverse events

Adverse events including SAEs, AESIs, and EOSIs will be assessed. Refer to [Section 10.4](#) to [Section 10.7](#) for details.

9.2.1.1.1 Adverse events of special interest

Adverse events of special interest are listed in [Section 10.4.1.3](#), reporting requirements for AESI are presented in [Section 10.4.4](#).

9.2.1.1.2 Events of special interest

Events of special interest are separate from AESIs. For a list of events defined as EOSIs and their reporting requirements see [Section 10.4.1.4](#) and [Section 10.4.5](#), respectively.

9.2.1.2 Hypoglycemia

Hypoglycemia will be assessed from the signing of the ICF until 2 weeks after the last dose of IMP (note: for patients who discontinue treatment before Week 79, safety data will be collected until scheduled study end). Patients will also complete the hypoglycemia specific page (as part of the patient diary) from Visit 1 onwards, which will be regularly reviewed by Investigators. See [Section 10.6.1](#) for further details.

9.2.1.3 Laboratory safety variables

The clinical laboratory data consist of blood analysis (including hematology, clinical chemistry, amylase, lipase, lipid profile) and urinalysis, according to the schedule presented in [Section 1.2](#). Clinical laboratory values will be analyzed after conversion into standard international units. International units will be used in all listings and tables. [Table 2](#) lists the hematology, clinical chemistry, and other blood safety parameters to be assessed by the central laboratory.

In addition, for WOCBP a serum pregnancy test is performed at Screening, and urine pregnancy tests are taken at all on-site visits during the double-blind treatment period excluding Visit 4 (Week 1). Any positive urine test results must be confirmed by a serum pregnancy test. The Investigator may perform additional tests at their discretion or as required by local regulations.

Serum follicle-stimulating hormone (FSH) and estradiol will be measured in menopausal women at Screening (Visit 1, Week -4) (see [Appendix A](#) for definition of menopausal women).

Table 2 - Blood safety parameters

Clinical chemistry	Hematology	Other blood parameters
Sodium	Complete blood count (CBC)	Lipid profile
Potassium	Differential	Total cholesterol (TC)
Chloride	Platelet count	High-density lipoprotein cholesterol (HDL-C)
Carbon dioxide (bicarbonate)	Hemoglobin	Low-density lipoprotein cholesterol (LDL-C) will be calculated by Friedwald equation
Blood urea nitrogen (BUN)	Hematocrit	Non-HDLC will be calculated as the difference between TC and HDLC
Creatinine (eGFR will be calculated)		Triglycerides (TG)
Glucose (serum)		Other chemistry tests
Alanine aminotransferase (ALT)		
Aspartate aminotransferase (AST)		
Total bilirubin (TB)		
Alkaline phosphatase (ALP)		
Uric acid		
Calcium		
Phosphorus		
Total protein		
Albumin		
Magnesium		
Creatine phosphokinase (CPK)		
Lactic acid dehydrogenase (LDH)		
Amylase		
Lipase		

All assessments to be performed by central laboratory. All assessments measured in serum.

9.2.1.3.1 Urinalysis

Urinalysis (urine dipstick with microscopy) will be performed by central laboratory at Screening (Visit 1), Baseline (Visit 3), Week 26 (Visit 9), and Week 79 (Visit 13). To prevent partial unblinding, the central laboratory urinalysis dipstick will not include the measurement of urine glucose. Central urinalysis includes:

- Urine dipstick includes: specific gravity, pH, protein, blood, ketones, bilirubin, urobilinogen, nitrite, and leukocyte esterase
- Urine microscopy includes, but is not limited to: detection of formed cellular elements, casts, bacteria, yeast, parasites, and crystals in centrifuged urine sediment

In the event of abnormal urinalysis findings, suspicious of urinary tract infection, urine culture should be performed. Additionally, urine culture should be performed if at any point the PI suspects the presence of a urinary tract infection. If the urine dipstick is positive for blood, the central laboratory will perform reflexive testing to include microscopy. Additional testing will be performed according to the judgment of the Investigator. Referral to urology/urologic evaluation is recommended for new or unexplained cases of confirmed hematuria (urology/urologic evaluation is not required where hematuria is considered to be related to diabetic nephropathy).

9.2.1.4 Vital signs and physical exam

A complete physical exam (including sitting BP and heart rate, temperature and respiratory rate) will be performed at Visit 1 (Screening), Visit 9 (Week 26), and Visit 13 (Week 79). Abbreviated physical exams (including sitting BP and heart rate) will be performed at all other on-site visits. The abbreviated physical exam should focus on cardiac and respiratory systems, as well as any areas important for assessment of AEs if necessary.

Three separate seated BPs and heart rate measurements should be taken with at least 1 minute between measurements following a 5-minute rest period, and prior to phlebotomy. Full details and directions for the measurement of BP are presented in [Appendix C](#).

9.2.1.5 Electrocardiogram variables

The ECG assessment of “normal” or “abnormal” will be analyzed.

A 12-lead ECG record is performed locally at Screening (Visit 1), Week 26 (Visit 9), and Week 79 (Visit 13).

The 12-lead ECG should be performed after at least 10 minutes in a supine position and prior to IMP administration. The Investigator should review the ECG and document the interpretation, sign and date it on the ECG print out and report it in the e-CRF. Each ECG trace is analyzed in comparison with the screening recorded trace. All original traces are kept as source data.

Note: Any new ECG abnormality should be rechecked for confirmation and reported as appropriate for that finding.

9.2.1.6 Self-monitoring of blood glucose

A meter for self-assessment of blood glucose will be dispensed at the Run-in visit (Visit 2). In addition to home measurements of self-monitored blood glucose, self-monitoring of blood glucose will be performed at the Run-in Visit (Visit 2), Baseline (Visit 3) and all subsequent on-site visits. Glucose meters used for SMBG display results as plasma glucose concentration.

Patients will also receive a patient diary at all on-site visits with the exception of Visit 13 (End of Treatment visit). The diary will be reviewed at all on-site visits from Visit 2 to Visit 13. Self-assessed blood glucose levels will be entered in the patient diary.

Patients will be asked to self-assess fasting blood glucose levels at least 3 times a week from the Run-in Visit (Visit 2) to the end of the Treatment Period including on day of each on-site study visit. After Visit 9 (Week 26), if SMBG values are <120 mg/dL over a two-week period, the Investigator can (at their own discretion) instruct patients to self-monitor blood glucose once a week (on day of on-site study visit for weeks with on-site study visits).

Patients will also be requested to self-assess blood glucose levels whenever they experience any illnesses (eg, cold, flu), or symptoms of hyperglycemia or hypoglycemia. Symptoms of hypoglycemia may include shakiness, dizziness, sweating, hunger, headache, pale skin color, sudden moodiness or behavior changes (such as crying for no apparent reason), clumsy or jerky movements, seizure, difficulty paying attention or confusion, or tingling sensations around the mouth. Patients will be instructed to record the presence or absence of hypoglycemic episodes or hypoglycemic symptoms in the patient diary provided.

Patients will also be instructed to record SMBG values that are ≤ 70 mg/dL (≤ 3.9 mmol/L) in the patient diary. Patients should be instructed to contact the site if fasting SMBG values over 3 consecutive days are:

- >270 mg/dL (15.0 mmol/L) from Randomization up through the scheduled Week 8 Visit
- >240 mg/dL (13.3 mmol/L) after the Week 8 visit up through the scheduled Week 12 Visit
- >200 mg/dL (11.1 mmol/L) after the Week 12 Visit and through the end of the 26-week double-blind Core Treatment Period
- >170 mg/dL (9.4 mmol/L) after the Week 26 Visit through the end of the Extension treatment period

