- f The abbreviated physical exam should focus on cardiac and respiratory systems, as well as any areas important for assessment of adverse events if necessary.
- g See [Section 9.2.1.6](#) for details of SMBG measurements. Glucose meters used for SMBG display results as plasma glucose concentration. Patients should measure their fasting plasma glucose at least 3 times per week (including on day of each on-site study visit). After Visit 9 (Week 26), if fasting SMBG values are <120 mg/dL, over a 2-week period, the Investigator can instruct patients to self-monitor blood glucose once a week (on day of on-site study visit for weeks with on-site study visits).
- h The 12-lead electrocardiogram (ECG) recordings should be obtained prior to IMP administration. The ECG will be evaluated as “normal” or “abnormal”.
- i All laboratory assessments occur prior to IMP administration on the day of the visit.
- j Clinical chemistry, hematology: please see list in [Table 2](#).

- k* Serum pregnancy testing only at screening; urine pregnancy testing subsequently. Serum pregnancy test results must be reviewed prior to the Run-In phase for all women of childbearing potential (WOCBP) unless there is documented history of menopause (based on documented follicle-stimulating hormone [FSH] and estradiol levels – if results not documented then FSH and estradiol will be tested at Screening visit) or they are surgically sterile. Any positive urine test results must be confirmed based on serum pregnancy test. The Investigator may perform additional tests at their discretion or as required by local regulations.
- l* Pre-dose plasma concentration samples (ie, of sotagliflozin and sotagliflozin-3-O-glucuronide) should be drawn with the other laboratory assessments at Week 4, Week 18, Week, 26, Week 52, and Week 79. Post-dose plasma concentration samples should be drawn 1 hour 30 minutes after sotagliflozin administration at Week 26 and Week 79. The date and time of the last intake of study drug prior to visits where pharmacokinetic (PK) samples are taken should be recorded by the patient in the patient diary. Patients should be reminded of this at visits preceding PK time points to ensure these details are captured. In the case of premature IMP discontinuation, PK samples should not be drawn at the premature EOT visit, nor at any subsequent visits.

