4.2 CLINICAL TRIALS OF SOTAGLIFLOZIN IN HUMANS

Approximately 780 subjects (639 assigned to sotagliflozin and 141 assigned to placebo) have participated in completed clinical studies of sotagliflozin. No significant safety concerns have been identified in the sotagliflozin drug program, and sotagliflozin has been well-tolerated in all studies to date. Serious adverse events (SAEs) and discontinuations due to adverse events (AEs) have been infrequent and have been balanced between treatment and comparator groups. Reports of treatment-emergent adverse events (TEAE) across all sotagliflozin studies for which data are available were generally balanced between treatment and comparator groups. The most frequently reported TEAEs ($\geq 2.0\%$) were headache, nausea, diarrhea, constipation, and dizziness, all of which were reported at a frequency greater than placebo. However, the majority were described as mild to moderate, and most resolved spontaneously.

In completed and ongoing clinical trials, no safety issues in addition to those already described in the current Investigator's Brochure (IB) were observed. In general, no significant imbalances of SAE/AEs between sotagliflozin and comparators were observed in completed studies. Cumulatively, during the clinical trial program 8 SAEs were reported by 6 patients (4 T2D and

2 T1D), all of which were assessed as unrelated to study drug; those reported by 4 T2D patients who received sotagliflozin included pulmonary embolism, deep vein thrombosis, bile duct stone, cholangitis and lower limb fracture, while a myocardial infarction (MI) was experienced by a patient receiving placebo. Two SAEs of diabetic ketoacidosis (DKA) were reported by 2 T1D patients receiving 400 mg once daily sotagliflozin in the Phase 2 T1D study LX4211.1-203-TIDM; both SAEs were assessed as due to failure of insulin delivery via insulin pump.

Inhibition of SGLT2 and SGLT1 is expected to improve glycemic control, but may also potentially increase the risk of hypoglycemia when given with insulin or insulin secretagogues like sulfonylurea. Other medicines in the SGLT2 class have had a low incidence of hypoglycemia in general, but when used in combination with insulin or insulin secretagogues, an increase in hypoglycemia has been observed.

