5.2 SECONDARY

- To compare sotagliflozin 400 mg versus placebo for:
 - Change from Baseline in FPG at Week 26
 - Change from Baseline in body weight at Week 26
 - Change from Baseline in SBP at Week 12 for patients with Baseline SBP \geq 130 mmHg
 - Change from Baseline in SBP at Week 12 for all patients
 - Proportion of patients with HbA1c $<$ 6.5%, $<$ 7.0% at Week 26
- To evaluate the safety of sotagliflozin 400 mg versus placebo throughout the 79-week trial

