#### **2.4.5.1 Analyses of hypoglycemia**

Analyses of hypoglycemia will be performed on the TEAE periods as defined in [Section 2.1.4](#). Hypoglycemia will be classified as severe hypoglycemia, documented symptomatic hypoglycemia, asymptomatic hypoglycemia, probable symptomatic hypoglycemia or relative hypoglycemia [Section 2.1.4.1](#).

The number (%) of patients with any hypoglycemia, severe hypoglycemia, and documented symptomatic hypoglycemia will be summarized respectively by treatment group during the TEAE period, as well as the incidence rate in patient years. Two types of incidence rates will be presented: the number of patients with at least 1 event per 100 patient years (calculated as the number of patients with at least 1 event / total exposure in 100 patient years), and the number of events per 100 patient-years [calculated as the total number of events / (total exposure in 100 patient-years)]. Note: here exposure (in days) is duration of TEAE period, ie, duration of IMP treatment in days +1 (Section 2.1.4).

The summary of frequency and incidence rate in patient years for severe hypoglycemia or documented symptomatic hypoglycemia will be provided as appropriate by gender (Male, Female), age group (<50, ≥50 to <65, ≥65 years), race (White, Black or African American, Asian, Other) and Metformin use at Screening (Yes, No).

A KM curve will also be provided by treatment group for the time to first severe hypoglycemia or documented symptomatic hypoglycemia during the TEAE period for the 79-week entire treatment period only.

Documented symptomatic hypoglycemia maybe presented by  $\leq 3.9$  mmol/L ( $\leq 70$  mg/dL) and  $< 3.0$  mmol/L ( $< 54$  mg/dL) respectively, as appropriate.

A listing of patients for all events reported on the dedicated e-CRF “Hypoglycemic event information” page will be provided with each category flagged (ie, severe hypoglycemia, documented symptomatic hypoglycemia, asymptomatic hypoglycemia, probable symptomatic hypoglycemia and relative hypoglycemia).

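### After Week 26 routine glucose self-testing may be reduced only in patients with well-controlled readings, so the 79-week summary of 'any' hypoglycaemia can depend on treatment response

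*Protocol*

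**What the plan says.** **Testing schedule.** Protocol 9.2.1.6 asks patients to measure fasting glucose "at least 3 times a week from the Run-in Visit (Visit 2) to the end of the Treatment Period". The next sentence makes an exception: "After Visit 9 (Week 26), if SMBG values are <120 mg/dL over a two-week period", then "the Investigator can (at their own discretion) instruct patients to self-monitor blood glucose once a week". Footnote g of the flow chart (Protocol 1.2, repeated in SAP Appendix D) gives the same exception with the trigger worded as "if fasting SMBG values are <120 mg/dL, over a 2-week period". Testing on symptoms is kept: "Patients will also be requested to self-assess blood glucose levels whenever they experience any illnesses (eg, cold, flu), or symptoms of hyperglycemia or hypoglycemia".

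**Event definitions.** Under Protocol 10.6.1 and SAP 2.1.4.1 an asymptomatic event needs a measured plasma glucose of 70 mg/dL or less. A severe event needs no glucose value, and a probable symptomatic event is defined by the absence of one.

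**Analysis.** SAP 2.4.5.1 states: "The number (%) of patients with any hypoglycemia, severe hypoglycemia, and documented symptomatic hypoglycemia will be summarized respectively by treatment group". Rates are per 100 patient-years of exposure. Asymptomatic events are one of the five classes, so they enter 'any', but on their own they appear only as a flag in a listing. Safety is summarised for the 26-week core period and the 79-week entire period (SAP 2.4.5), descriptively and without tests. Neither document provides for recording or reporting who was moved to weekly testing, or when.

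**The concern.** The trigger for less testing is a glucose level reached after randomisation. Sotagliflozin is meant to lower glucose, and change in FPG is the first secondary endpoint in the testing order. If more sotagliflozin than placebo patients qualify, the active arm is searched less closely for asymptomatic lows. The rate denominator is exposure time, so fewer readings reduce the count of events and leave the denominator unchanged.

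Hypoglycaemia is also the risk that the protocol itself raises for this combination: Protocol 4.2 says that SGLT inhibition "may also potentially increase the risk of hypoglycemia when given with insulin or insulin secretagogues like sulfonylurea". A secondary objective is "To evaluate the safety of sotagliflozin 400 mg versus placebo throughout the 79-week trial", and 53 of those 79 weeks fall after the point at which testing may diverge. An attenuated 'any' comparison could be read as reassurance. The 26-week and 79-week tables will sit side by side, and Protocol 11.4.3.2 plans to look at the pattern of events over time. A fall caused by fewer readings could therefore pass for a real decline.

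**Working it through.** The plan states no figure for hypoglycaemia or for SMBG switching, so there is none to reproduce.

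**1. Readings per patient.** At three a week: 3 × 53 = 159 (a minimum). At one a week: 1 × 53 = 53. The cut is 1 − 53/159 = 67% for a patient switched for the whole Extension.

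**2. Model for the table that is planned.** Inputs from the documents: a cut to one third, and an Extension share W = 53/79 = 0.671. Assumed inputs:
- s = share of an arm's Extension asymptomatic events that arise in switched patients
- a = share of asymptomatic events among 'any', the same in both arms
- events spread evenly over the 79 weeks, with detection of asymptomatic events proportional to routine readings

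Detected share of asymptomatic events in the Extension: 1 − (2/3)s.

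Factor on the 0-79-week rate ratio for 'any': [1 − W·a·(2/3)·s_sota] / [1 − W·a·(2/3)·s_pbo].

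Worked case, s = 0.5 and 0.2, a = 0.5: (1 − 0.1118)/(1 − 0.0447) = 0.888/0.955 = 0.93.

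| s (sotagliflozin / placebo) | Asymptomatic, Extension only | 'Any' 0-79 wk, a = 0.3 | a = 0.5 | a = 0.7 |
|---|---|---|---|---|
| 0.3 / 0.1 | 0.86 | 0.97 | 0.95 | 0.94 |
| 0.5 / 0.2 | 0.77 | 0.96 | 0.93 | 0.90 |
| 0.8 / 0.2 | 0.54 | 0.92 | 0.86 | 0.80 |
| 0.2 / 0.2 | 1.00 | 1.00 | 1.00 | 1.00 |
| 0.3 / 0.4 | 1.09 | 1.01 | 1.02 | 1.04 |

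In the first three rows a true ratio of 1.5 would show as 1.46 (factor 0.97) down to 1.20 (factor 0.80). These are factors on event rates. The percentage of patients with at least one event moves in the same direction, but not by the same amount.

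**3. Can an excess disappear?** Assume that 30% of sotagliflozin and 10% of placebo patients are switched, and that switched patients carry three times the risk of the others. Relative true rates are 0.3 × 3 + 0.7 = 1.6 and 0.1 × 3 + 0.9 = 1.2, a ratio of 1.33. Relative detected Extension rates are 0.3 × 3/3 + 0.7 = 1.0 and 0.1 × 3/3 + 0.9 = 1.0, a ratio of 1.00. The planned table also contains the 26 unaffected weeks. If the true ratio is the same there and every event is asymptomatic, the 79-week ratio is (26 × 1.6 + 53 × 1.0)/(26 × 1.2 + 53 × 1.0) = 94.6/84.2 = 1.12. If half of all events are asymptomatic, it is (94.6 + 79 × 1.6)/(84.2 + 79 × 1.2) = 221.0/179.0 = 1.23.

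**4. Would censoring at the switch help?** In the same model unswitched patients have equal risk in both arms. A post-Week-26 rate censored at the switch therefore returns 1.00 against a true 1.33, which is the very distortion to be avoided.

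**The case against.** **The affected output is narrow.** No Extension-only comparison and no by-arm table of asymptomatic events is planned. Severe and documented symptomatic events rest on symptoms or symptom-triggered testing, and they are the categories used in the Kaplan-Meier curve. What remains is one descriptive summary, 'any' over 0-79 weeks. This stands, and the size is given for that summary.

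**Direction is not shown.** Switching is discretionary and its rate by arm is unknown. Rescue after Week 26, which may include insulin, could also bring placebo patients under 120 mg/dL. An Investigator who sees lows in the diary may decline to reduce testing, which weakens the threefold-risk assumption. The qualifying two weeks mean that few patients would be switched for all 53 weeks. All of this stands. Against it, the 12-week Phase 2b HbA1c falls were 0.93% on 400 mg and 0.14% on placebo (Protocol 4.3). Rescue after Week 26 also starts only from FPG above 170 mg/dL or HbA1c of at least 8.0%, well away from the trigger. More switching on sotagliflozin is the likelier case, but it remains an expectation.

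**Two stronger readings are tempting.** A reader might infer that a real excess would vanish from the 79-week tables. In step 3 a true 1.33 shrinks to 1.12 or 1.23. Even at the worst factor in the range, 0.80, only a true ratio of 1/0.80 = 1.25 or less would be hidden, and the documents do not supply the inputs for that case. A reader might also infer that 9.2.1.6 contradicts itself. It does not: it gives a general rule followed by an explicit exception.

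**Conclusion.** The point holds as a risk to one safety summary. A stated protocol rule lets the detection of asymptomatic hypoglycaemia, and through it 'any' hypoglycaemia, depend on treatment response after Week 26, and nothing in the SAP would reveal it. If more sotagliflozin patients are switched, the 0-79-week comparison of 'any' is pulled towards no excess by a factor of roughly 0.80 to 0.97. That range rests on assumed s from 0.3/0.1 to 0.8/0.2, assumed a from 0.3 to 0.7, and even spread of events over time. It does not support a statement that the Extension comparison is biased: no such table is planned, and neither the size nor the direction of any difference in switching is documented. The inclusion of asymptomatic events in 'any' is itself read from the SAP's classification, since 'any' is not defined separately.

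**What to change.** 1. **e-CRF:** record the date on which any patient's routine SMBG is reduced.
2. **SAP 2.4.5.1, testing intensity:** report by arm the number and timing of these reductions and, where captured, SMBG readings per patient-week after Week 26. Values are entered in the patient diary, but the documents do not say whether every reading reaches the database.
3. **SAP 2.4.5.1, events:** summarise asymptomatic and 'any' hypoglycaemia by arm separately for Weeks 0-26 and after Week 26. Do not censor at the switch, for the reason in step 4 of the working.
4. **Interpretation:** state in advance that Weeks 0-26 are the comparison with a uniform testing rule, and that conclusions after Week 26 rest on severe and documented symptomatic events.
5. **Protocol wording:** the sponsor should reconcile the trigger in 9.2.1.6, which omits the word fasting, with footnote g, which includes it. The sponsor should also consider whether the testing schedule that feeds a safety endpoint should depend on post-randomisation glucose. No monitoring frequency is proposed here.

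Items 1 to 4 leave patient care unchanged and cost one e-CRF date, a small extra table and a sentence of interpretation.
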